11.1.4 Duration of Response

Duration of overall response: The duration of overall response is measured from the time measurement criteria are met for CR or PR (whichever is first recorded) until the first date that recurrent or progressive disease is objectively documented.

The duration of overall CR is measured from the time measurement criteria are first met for CR until the first date that progressive disease is objectively documented.

Duration of stable disease: Stable disease is measured from the start of the treatment until the criteria for progression are met, taking as reference the smallest measurements recorded since the treatment started, including the baseline measurements.

11.1.5 Progression-Free Survival

PFS is defined as the duration of time from start of treatment to time of progression or death, whichever occurs first.

12. DATA REPORTING / REGULATORY REQUIREMENTS

Adverse event lists, guidelines, and instructions for AE reporting can be found in Section 6.0 (Adverse Events: List and Reporting Requirements).

12.1 Patient Protection

The study will be conducted in accordance with the ethical principles of the Declaration of Helsinki and the ICH-GCP guidelines. The Principal Investigator is responsible for ensuring that the study will be conducted in accordance with the protocol, the ethical principles of the Declaration of Helsinki, current ICH guidelines on Good Clinical practice (GCP) and applicable local regulatory requirements.

12.2 Patient Information

Before entry into the trial all eligible patients will receive written patient information describing the aim of the study, as well as probable and possible side effects and risks. Oral information from one of the investigators or a delegated person at the institution will also be given, and the patient must have the opportunity to ask questions, and to consider participation together with his/her family members if applicable. It will be emphasized that the participation is voluntary and that it is the right of the patient to refuse further participation in the study whenever he/she wants and that this will not influence his/her subsequent care.

12.3 Informed Consent

Patient / legally acceptable representative (as applicable) written consent must be obtained according to local Institutional Review Board requirements and must conform to the ICH guidelines for Good Clinical Practice, prior to any study-specific screening procedures and trial entry. The written informed consent form should be signed and personally dated by the patient or by the patient's legally acceptable representative. A copy of the signed informed consent will be given to the patient or patient's legally authorized representative. The original signed consent must be maintained by the Investigator at each participating site and available for inspection by regulatory authority at any time. A copy of all external participating site consents must also be sent to the OSU Multi-Institution Program Coordinator to be filed in the OSU multi-institution regulatory files.

12.4 Data Submission

The study will be managed per the Multi-Center Trial Program (MCTP) policies. Subsite data must be submitted to the MCTP as outlined in the protocol-specific monitoring plan, which will be provided to external participating sites. Data will be submitted using case report forms and the Data Submission Form cover sheet (refer to Supplemental Forms Document) supplied by the MCTP. All data submitted must be accompanied by supporting source documents, where applicable and as outlined in the protocol-specific monitoring plan.

13. STATISTICAL CONSIDERATIONS

13.1 Study Design

Cohorts 1 and 2 of this study represent a prospective, multi-center, phase I dose escalation study in two diseases: CLL and NHL. Dose-finding will proceed using a modified continual reassessment method and targeting a probability of $DLT < 0.30$. To ensure safety, the starting dose level will be the lowest dose level and dose escalation will proceed by increasing only one dose level at a time. Groups of 2-3 patients will be treated until convergence on an MTD, defined as 10-12 patients treated at a particular dose level which is also a subsequently suggested dose level by the model *or* a maximum of 36 evaluable patients, whichever occurs first. At the MTD, up to 10 CLL patients and 10 NHL patients will be accrued.

13.2 Sample Size/Accrual Rate

For cohort 1 and 2, with groups of 2-3 patients per month enrolled in the dose finding study, it is expected that approximately 9 groups of patients will be treated over 18-30 months. Expansion at the MTD is expected to accrue over 6-12 months. Thus, the total study duration is estimated to be 24-42 months. On average, we expect 32 patients to be enrolled, but the total sample size could be as many as 50 patients and will depend on the dose escalation and composition of CLL and NHL patients treated at the estimated MTD as part of the dose-finding portion of the study.

Cohort 3 will be a pilot study to gain data on the ability of selinexor to deepen responses with ibrutinib. Ten patients who have been treated with ibrutinib as their frontline therapy for CLL/SLL for at least 12 cycles and have obtained PR will be accrued to this cohort, and selinexor will be added to ibrutinib for 14 more cycles. The deepening of response rate is defined as the percentage of patients who convert to a MRD negative complete response (MRD- CR) from PR at the end of 14 cycles of selinexor plus ibrutinib among this cohort. If we observe 3 or more patients out of 10 who achieve the conversion from PR to MRD-CR, we will consider this regimen promising and move it forward for further study. For various true deepening of response rates, the table below shows the probability of observing at least 3 MRD-CRs in 10 patients. For example, if the true deepening response rate is 30%, then the probability of declaring the regimen promising is 61.7% with 10 patients.

True Deepening of Response Rate	Probability of Observing 3 or More MRD-CR in 10 Patients
0.1	0.070
0.2	0.322
0.25	0.474
0.3	0.617
0.35	0.738
0.4	0.833

With an accrual rate of 2 patients per month, we expect accrual to be complete in 5 months.

13.3 Evaluability

Any patient who is eligible for the trial and has received at least one dose each of the selinexor and ibrutinib will be evaluated for toxicity (descriptive summary as well as dose escalation determination in the first two cohorts) and for response. Patients who are not evaluable for toxicity at a given dose level will be replaced.

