5.2 Agent Administration

Treatment will be administered on an outpatient basis. Reported adverse events and potential risks are described in Section 7. Appropriate dose modifications are described in Section 5. No investigational or commercial agents or therapies other than those described below may be administered with the intent to treat the patient's malignancy.

Regimen Description					
Agent	Precautions	Dose	Route	Schedule	Cycle Length
Ibrutinib	Take with 8 oz of water, 30 min before meal	Capsule or tablet*	Oral	Cycle 1 Days 8-28**, Cycles 2+ Days 1-28	28 days (4 weeks)
Selinexor	Take with at least 120 mL (4 ounces) of fluids (water, juice, etc.)	Tablet*	Oral	Days 1, 8, and 15 of each cycle *	
*Doses/schedule as appropriate for assigned dose level.					
**Patients continuing on ibrutinib should take ibrutinib days 1-28 of Cycle 1					

Dose Level	Selinexor Dose	Selinexor Schedule	Ibrutinib Dose	Ibrutinib Schedule
1*	40 mg	Weekly (oral)	420 mg	Daily (oral)
2	20 mg	Bi-weekly (oral)	420 mg	Daily (oral)

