7.2 Recording of Adverse Events

All AE will be reported and recorded from the time of the first dose of study drug through 30 days after the last dose of study drug or until the start of subsequent antineoplastic therapy, whichever occurs first. That is, if a patient begins a new antineoplastic therapy, the AE reporting period for nonserious AEs ends at the time the new treatment is started.

AE monitoring should be continued for at least 30 days following the last dose of study treatment (i.e., through 30 days following last dose or until resolution or through the end of the study for events considered related to study treatment by the Investigator). AEs (including laboratory abnormalities that constitute AEs) should be described using a diagnosis whenever possible, rather than individual underlying signs and symptoms. When a clear diagnosis cannot be identified, each sign or symptom should be recorded as a separate AE.

The Investigator should ask the patient non-leading questions to determine if AEs occur during the study. AEs may also be recorded when they are volunteered by the patient, or through physical examination, laboratory tests, or other clinical assessments.

An AE should be followed until its resolution or until it is judged to be permanent, and assessment should be made at each visit (or more frequently, if necessary) of any changes in severity of the event, the suspected relationship to the study treatment, the interventions required to treat the event, and the outcome.

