11.1.1 Definitions

Evaluable for toxicity. All patients will be evaluable for toxicity from the time of their first treatment with selinexor.

Evaluable for response. Only those patients who have received at least four weeks of therapy and have had their disease re-evaluated will be considered evaluable for response. These patients will have their response classified according to the definitions stated below. (Note: Patients who exhibit objective disease progression prior to the end of 4 weeks will also be considered evaluable.)

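### Section 13.3 limits the toxicity summary to eligible patients who took both drugs, contradicting 11.1.1 and dropping some treated patients, including those stopped by toxicity before ibrutinib

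*Combined protocol and SAP*

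**What the plan says.** Section 13.3 sets the population: "Any patient who is eligible for the trial and has received at least one dose each of the selinexor and ibrutinib". It applies this one set to three uses: the descriptive toxicity tables, the dose-escalation decisions in Cohorts 1 and 2, and the response analysis. On patients outside the set it says: "Patients who are not evaluable for toxicity at a given dose level will be replaced".

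Section 11.1.1 sets a different one: "All patients will be evaluable for toxicity from the time of their first treatment with selinexor". It attaches no condition on eligibility or on ibrutinib.

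Section 7.2 starts adverse event collection at the first dose: "All AE will be reported and recorded from the time of the first dose of study drug". Section 13.8.1, which plans the toxicity tables for secondary objective 1.2.1, names no population.

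In the regimen table of Section 5.2, selinexor is given on "Days 1, 8, and 15 of each cycle" and ibrutinib on "Cycle 1 Days 8-28, Cycles 2+ Days 1-28". A footnote makes an exception: "Patients continuing on ibrutinib should take ibrutinib days 1-28 of Cycle 1". Section 6 says that a DLT in Cycle 1 leads to removal from the protocol.

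**The concern.** A safety summary normally covers everyone exposed to the investigational drug. Section 13.3 adds two conditions: the patient must be eligible, and must also have taken ibrutinib. The second is the more serious. A patient not already on ibrutinib spends the first week on selinexor alone, so whether that patient enters the set depends on getting through the week without death, removal or withdrawal. Selection on the outcome removes early, severe selinexor toxicity from the tables that are meant to describe it.

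At stake is secondary objective 1.2.1, the safety and tolerability of the combination. The number of patients is small enough that one omitted fatality or serious event changes how the regimen reads. With two conflicting definitions in one document, the analyst could also choose between them after seeing the data.

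**Working it through.** There is no figure in the plan to reproduce, because the point is about a definition. The check compares the passages and then illustrates the size.

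**1. Do the two definitions differ?**

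| | 13.3 | 11.1.1 |
|---|---|---|
| Must be eligible | Yes | No |
| Selinexor | At least one dose | From first treatment |
| Ibrutinib | At least one dose | No condition |
| Stated use | Descriptive summary, dose escalation (first two cohorts), response | Toxicity |

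They do. Because 13.8.1 names no set, the only toxicity population in the statistical section is the narrower one.

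**2. Is 13.3 a restriction?** Its opening word is inclusive, but its next sentence provides for replacing patients who are not evaluable for toxicity. That makes sense only if some treated patients fall outside the set.

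**3. Who falls outside?**

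- Treated patients later found ineligible. This can occur in any cohort.
- Day 8 ibrutinib starters who never reach ibrutinib. Selinexor begins on Day 1 and ibrutinib on Day 8, so 8 − 1 = 7 of the 28 Cycle 1 days precede any ibrutinib. On the Days 1, 8, 15 schedule, 1 of 3 Cycle 1 selinexor doses falls in that week. A Grade 5 toxicity is a DLT under 5.3 unless clearly unrelated to study drug, and Section 6 removes patients with a Cycle 1 DLT. Such a patient meets 11.1.1 and fails 13.3.

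**4. Effect on a reported rate (counts assumed, not from the documents).** Exact 95% limits for x events in n patients are the 0.025 quantile of Beta(x, n − x + 1) and the 0.975 quantile of Beta(x + 1, n − x). One excluded patient who had the event changes x/n to (x − 1)/(n − 1).

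- Five Grade 3 or higher events in 20 treated: 5/20 = 25.0% (8.7-49.1%).
- One of the five excluded: 4/19 = 21.1% (6.1-45.6%), a fall of 25.0 − 21.1 = 3.9 percentage points.
- One early death in 20 treated: 1/20 = 5%. Excluded: 0/19 = 0%.

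**5. How often might it happen?** The documents give no rate of stopping in Days 1-7. Take q as that probability, and N = 32, the enrolment 13.2 expects on average for Cohorts 1 and 2. Suppose all 32 were new ibrutinib starters, which makes these upper figures for that enrolment. Expected losses are N × q, and the chance of losing at least one is 1 − (1 − q)^N.

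| q | Expected lost | Chance of at least one |
|---|---|---|
| 2% | 0.6 | 48% |
| 5% | 1.6 | 81% |
| 10% | 3.2 | 97% |

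**The case against.** The strongest reply is that this is an unreconciled inconsistency, not a settled exclusion. Section 13.3 does not say *only*, whereas 11.1.1 does use that word when it restricts the response set. Section 11.1.1 already states the inclusive toxicity rule, and the replacement sentence in 13.3 speaks of a given dose level, which is dose-finding language. The sponsor may well intend the wider set. That does not rescue 13.3: it names the descriptive summary in the same sentence, and 13.8.1 does not point back to 11.1.1.

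Several limits on reach do stand:

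- The Day 1-7 route cannot arise in Cohort 3 or in anyone else continuing ibrutinib.
- It is narrow. Several DLT categories in 5.3 require at least 7 days' duration, so few could be established before Day 8. A patient who only interrupts or reduces selinexor may still start ibrutinib. What remains is death, a DLT without a duration condition, or withdrawal within the week.
- The ineligibility route does not depend on outcome. It should be uncommon, since Section 4 requires entry criteria to be met before registration and subsite eligibility to be verified centrally.
- The 1-in-3 dose count fits weekly dosing. Section 5.2.3 also describes a twice-weekly dose level.
- Adverse events are still recorded, and serious ones still reported and reviewed by the DSMC. The loss is from the summary tables, not from collection or oversight.
- The illustrative intervals overlap almost entirely, so the shift in a percentage is modest. The loss of an individual death or serious event is the larger harm.

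**Conclusion.** The concern holds. Applied as written, Section 13 excludes some treated patients from the toxicity tables and contradicts 11.1.1. For Day 8 ibrutinib starters the exclusion is driven by early toxicity, so any resulting bias is downward. Section 13.5.2 includes everyone with at least one dose of study medication in ORR and PFS, so the safety set would be narrower than the efficacy set, which is hard to defend.

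The likely effect is small in percentage terms: about 4 points for one patient in 20 under the assumed counts. It could still remove a fatality from the table. The actual effect depends on the number of new ibrutinib starters and their rate of stopping in Days 1-7, neither of which the documents give. This should be corrected, but it does not invalidate the trial.

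**What to change.** In 13.3, define the safety set as all patients who received at least one dose of selinexor, regardless of later eligibility findings and of whether ibrutinib was started. Name that set in 13.8.1 as the population for the toxicity tables, matching 11.1.1.

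Take dose-escalation evaluability out of the same sentence and define the DLT set on its own, reconciled with the dose-count rule in 5.3. Exposure to ibrutinib can be shown as a column or footnote in the safety tables, so that events on selinexor alone remain identifiable.

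The cost is about a sentence in 13.3 and a reference in 13.8.1. No new data are needed, since 7.2 already collects events from the first dose. Reported toxicity may look slightly less favourable.

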13.4 Definition of Primary Endpoint

The primary endpoint is DLT. DLT has been defined in Section 4.2 above.

13.5 Definition of Secondary Endpoints

13.5.1 Toxicity will be graded by CTCAEv4.0. A copy of the CTCAE version 4.0 can be downloaded from the CTEP web site
http://ctep.cancer.gov/protocolDevelopment/electronic_applications/ctc.htm.

13.5.2 Clinical response and survival will be measured by:

- International Working Group Criteria for NHL patients.
- IWCLL 2008 Guidelines for CLL patients.

Response criteria are detailed in Section 10.

Responders will be defined as those with complete response (CR) or partial response (PR). Overall response rate (ORR) will be calculated as the number of evaluable responders divided by the total number of evaluable patients and will be analyzed by cohort. All patients who receive at least one dose of study medication will be included in the ORR and progression free survival.

Progression Free Survival (PFS): PFS will be calculated from the date of study enrollment to disease progression or death, whichever occurs first. Patients who do not progress or die will be censored at the time of last contact with response assessment by physical exam and laboratory studies.

Overall Survival (OS): OS will be calculated from the date of study enrollment to death. Patients who do not die will be censored at the time of last contact. This will be analyzed in each cohort independently.

13.5.3 Response as related to chronic lymphocytic leukemia (CLL) karyotype and IgVH mutational status. Response criteria are detailed in Section 10.

13.5.4 For Cohort 3, the rate of deepening of response is defined as the percentage of patients who attain a MRD negative complete response (MRD- CR) at the end of 14 cycles of selinexor plus ibrutinib.

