3.2 Exclusion Criteria

- 3.2.1 Patients who are concurrently receiving any other investigational agents.
- 3.2.2 Patients who have received:
- Radiation or chemotherapy \leq 4 weeks,
 - Mitomycin C, nitrosureas, or radio-immunotherapy \leq 6 weeks, or
 - Immunotherapy or targeted therapy (such as kinase inhibitors) \leq 2 weeks prior to cycle 1 day 1. Patients who are on ibrutinib at study entry are not required to discontinue ibrutinib for any period of time.
- Palliative steroids for disease related symptoms are allowed as long as dose is tapered down to an equivalent of \leq 10mg of oral prednisone daily on cycle 1 day 1.
- 3.2.3 Patients who have underwent autologous or allogeneic stem cell transplant \leq 4 weeks prior to cycle 1 day 1 or have active graft-versus-host disease are excluded.

- 3.2.4 Patients unable to swallow tablets or capsules, those with uncontrolled vomiting or diarrhea or disease significantly affecting gastrointestinal function and/or inhibiting small intestine absorption such as; malabsorption syndrome, resection of the small bowel, or poorly controlled inflammatory bowel disease affecting the small intestine
- 3.2.5 Patients who are 20% below their ideal body weight (BMI calculator can be found at http://www.cdc.gov/healthyweight/assessing/bmi/adult_bmi/english_bmi_calculator/bmi_calculator.html)
- 3.2.6 Patients must not be receiving systemic anticoagulation with warfarin. Patients must be off warfarin for 30 days prior to enrollment. Patients who require anticoagulation with an agent other than warfarin will not be excluded, but must be reviewed by the principal investigator prior to enrollment.
- 3.2.7 As ibrutinib is extensively metabolized by CYP3A4/5, and patients must not require continued therapy with a strong inhibitor or inducer of CYP3A4/5. See Appendix B for a list of these medications.
- 3.2.8 Patients with active HIV or Hepatitis C. (HIV-positive patients on combination antiretroviral therapy or Hepatitis C-positive patients on antiviral therapy are ineligible because of the potential for pharmacokinetic interactions with ibrutinib or selinexor. In addition, HIV patients are at increased risk of lethal infections when treated with potentially marrow-suppressive therapy.)

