6. DOSING DELAYS/DOSE MODIFICATIONS

Toxicities that occur in cycle 1 that are DLTs (Section 4.2) will result in protocol removal. Adverse events that are not defined as DLTs and / or occur in cycles 2 and higher will lead to dose delays and modifications as detailed below. No dose reduction below ibrutinib 140 mg and selinexor 20 mg/week will be allowed. If a patient experiences several adverse events, and there are conflicting recommendations, the investigator should use the recommended dose adjustment that reduces the dose to the lowest level. Missed doses will not be replaced. Treatment delays for adverse events exceeding 28 days will lead to protocol removal unless approved by the principal investigator.

Ibrutinib-related lymphocytosis, for the purposes of this protocol, is defined as an elevation in blood lymphocyte count of $\geq 50\%$ compared with baseline count in conjunction with unequivocal improvement in at least 1 other disease-related parameter including lymph node size, spleen size,

hematologic parameters (hemoglobin or platelets), or disease-related symptoms. Ibrutinib-associated treatment-related lymphocytosis generally occurs within the first few weeks of therapy, peaks within the first few months, and resolves slowly. Patients with isolated lymphocytosis in the setting of reduced disease burden or improvement in hemoglobin/platelets should not be considered to have progressive disease.

Asymptomatic treatment-related lymphocytosis should not be considered an adverse event. Subjects with treatment-related lymphocytosis in the absence of other disease-related symptoms should be encouraged to remain on study treatment and continue with all study-related procedures.

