13.7 Analytic Plan for Primary Objective

The primary objective is to identify the highest dose level of selinexor administered with ibrutinib that corresponds to an acceptable probability of DLT, defined as <0.30, in relapsed/refractory CLL and NHL patients. We do not expect that toxicity will be different between CLL and NHL, thereby justifying the use of both groups in dose escalation. Dosing

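### The ORR denominator is defined in conflicting ways, and the four-week rule in 11.1.1, if applied, would bias the rate upward by dropping early toxicity removals

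*Combined protocol and SAP*

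**What the plan says.** Three sections bear on who enters the ORR denominator.

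- **Section 13.5.2** gives the formula: "Overall response rate (ORR) will be calculated as the number of evaluable responders divided by the total number of evaluable patients". Shortly after, it adds: "All patients who receive at least one dose of study medication will be included in the ORR and progression free survival".
- **Section 13.3** says that an eligible patient who "has received at least one dose each of the selinexor and ibrutinib will be evaluated for toxicity"; the same sentence goes on to cover response.
- **Section 11.1.1** sets its own test for entering the response analysis: "Only those patients who have received at least four weeks of therapy and have had their disease re-evaluated will be considered evaluable for response". It makes one exception: "Patients who exhibit objective disease progression prior to the end of 4 weeks will also be considered evaluable".

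Section 6 adds a rule that interacts with these: "Toxicities that occur in cycle 1 that are DLTs (Section 4.2) will result in protocol removal" (the toxicity definition itself is in Section 5.3).

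Section 13.8.2 presents ORR for patients treated at the MTD with an exact 95% confidence interval, and summarises degree of response by disease group and dose level. The plan sets no null rate, target or power for ORR in Cohorts 1 and 2.

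**The concern.** The formula in 13.5.2 turns on the word evaluable, and the documents give it more than one meaning. An analyst who looks for a definition of evaluability for response finds it under that label only in 11.1.1, which is the most restrictive rule. An analyst who stays within Section 13 finds two broader rules that also differ from each other.

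The choice is not neutral. The 11.1.1 rule retains patients who fail early through progression but not those who fail early through toxicity, death or withdrawal. The second kind of failure matters in a dose-finding trial of a combination. ORR at the MTD is one of the efficacy summaries that would inform the randomized phase II work anticipated in Section 2.10. With up to 10 patients per disease group in the expansion, moving two or three patients out of the denominator changes the rate visibly. If the rule is settled after the data are seen, the choice could also be influenced by the result.

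**Working it through.** **Step 1: no planned figure to reproduce.** The documents state no expected ORR or sample-size calculation for it. The only response probabilities given are those in the Cohort 3 table (Section 13.2). An exact binomial calculation reproduces all six, for example 0.617 at a true rate of 0.30, and this point does not affect them.

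**Step 2: the rules side by side**, for eligible patients.

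| Patient | 13.5.2, one-dose sentence | 13.3 | 11.1.1 |
|---|---|---|---|
| Not on ibrutinib at entry, stops during week 1 without progression | in | out | out |
| Took both drugs, removed for a cycle 1 DLT | in | in | generally out |
| Took both drugs, dies or withdraws before re-evaluation, no objective progression | in | in | out |
| Took both drugs, objective progression before four weeks | in | in | in |
| Four weeks of therapy and re-evaluated | in | in | in |

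The first row arises because patients not already on ibrutinib start it on Day 8 of Cycle 1 (Section 5.2). The second arises because a cycle lasts 28 days. A patient removed during cycle 1 will usually have had less than four weeks of therapy, so an off-treatment scan would not by itself restore evaluability under 11.1.1.

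**Step 3: size of the effect if 11.1.1 is used.** Let n be the patients treated, r the responders, d those dropped, and f = d/n. Assume that none of those dropped is a responder.

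- All treated: r/n
- Four-week set: r/(n - d)
- Ratio: n/(n - d) = 1/(1 - f)

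The number dropped is not given, so f is assumed to run from 0 to 0.30. The upper end is borrowed from the dose-finding criterion in Section 13.7, an "acceptable probability of DLT, defined as <0.30". It is a reference point rather than a limit on f, since deaths and withdrawals would add to DLT removals.

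With n = 10 (one disease group in the expansion) and an assumed r = 5:

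| Dropped | ORR | Exact 95% CI | Ratio to all treated |
|---|---|---|---|
| 0 | 5/10 = 50.0% | 18.7 to 81.3% | 1.00 |
| 1 | 5/9 = 55.6% | 21.2 to 86.3% | 1/0.9 = 1.11 |
| 2 | 5/8 = 62.5% | 24.5 to 91.5% | 1/0.8 = 1.25 |
| 3 | 5/7 = 71.4% | 29.0 to 96.3% | 1/0.7 = 1.43 |

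**Step 4: case mix, a separate and lesser matter.** Section 3.2.2 states: "Patients who are on ibrutinib at study entry are not required to discontinue ibrutinib for any period of time". That sentence is not limited to Cohort 3, so Cohorts 1 and 2 can mix ibrutinib-naive and ibrutinib-continuing patients. For CLL, take the 71% quoted in Section 2.3 for ibrutinib alone as a proxy for naive patients. Take the 21% partial response rate quoted in Section 2.9 for selinexor alone in B-cell malignancies (14 of 68) as an assumed proxy for continuing patients. With naive share m, the pooled rate is 0.71m + 0.21(1 - m):

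- m = 1: 71%
- m = 0.75: 58.5%
- m = 0.5: 46%
- m = 0.25: 33.5%
- m = 0: 21%

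If continuing patients are instead given 50% (the 2 of 4 CLL patients in Section 2.9, nodal responses only), the range is 50 to 71%. In both cases pooling lowers the rate relative to naive patients.

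**The case against.** The strongest reply is that Section 13 has its own evaluability section, which covers response and asks only for one dose of each drug, and that 13.5.2 itself goes on to include everyone with at least one dose. On that reading the statistical section governs, early toxicity removals stay in, and the two Section 13 rules differ only for the few patients who stop selinexor before ibrutinib starts. This is a fair reading and it makes the bias conditional. It does not remove the conflict: no section gives Section 13 precedence, and 11.1.1 is still the only place that defines the label evaluable for response.

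It can also be said that ORR here is descriptive, secondary and imprecise. In the example, the shift from 50% to 71% lies inside the all-treated interval of 18.7 to 81.3%. That stands as a comment on importance. But the shift is systematic rather than random, and an exact interval built on the wrong denominator does not allow for it.

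A reader might go further and infer that the planned ORR is inflated and uninterpretable, partly because Cohorts 1 and 2 pool patients with different ibrutinib histories. The documents do not support that:

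- Inflation follows only if 11.1.1 is applied and someone is dropped.
- Patients continuing ibrutinib in Cohorts 1 and 2 must have relapsed or refractory disease, so pooling would more likely pull the rate down.
- ORR is not the sole efficacy evidence at the MTD. Section 13.8.2 also plans Kaplan-Meier PFS and OS, and 13.5.2 puts every dosed patient into PFS.
- Efficacy is described as preliminary (Section 1.2), and comparison with ibrutinib alone is left to later randomized trials (Section 2.10).

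**Conclusion.** The conflict is established from the current text: 13.5.2, 13.3 and 11.1.1 select different patients for the same rate. The upward bias is conditional. It arises only under the 11.1.1 rule, equals a factor of 1/(1 - f), and is nil if no one is dropped. For assumed f of 10, 20 and 30% the relative increase is 11, 25 and 43%. These sizes assume that every dropped patient is a non-responder; any responder among them would make the increase smaller. The numbers of early removals and responders are not in the documents, so the figures show scale rather than estimate the trial's actual error.

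The dependence of ORR on ibrutinib history is real but secondary. It limits what the rate says about selinexor's contribution; it does not show that the rate is inflated.

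**What to change.** Write one rule and use it in 11.1.1, 13.3 and 13.5.2. The ORR denominator is every eligible patient who received at least one dose of study drug, and patients with no post-baseline response assessment count as non-responders. Keep the four-week set from 11.1.1 only as a labelled sensitivity analysis. State the number of patients in each set and the reason for every exclusion from the smaller one.

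The cost is a wording change; no new patients, visits or tests are needed. The downside is that the reported ORR may be lower.

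As an optional descriptive addition to 13.8.2, list responses by ibrutinib history in three separate groups: naive, previously stopped, and continuing. Patients who stopped after failing ibrutinib should not be combined with naive patients. For NHL, list responses by DLBCL subtype with MCL shown separately. This would carry through objective 1.2.3, since 13.5.3 covers only the CLL markers. Prior-therapy dates and the ABC/GCB classification are already collected under the study calendar. Given the small numbers, show counts only.
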